### C. Study Design and Research Methods

This study is a preliminary investigation using a pre-post training design in six SNFs (Figure 1). We will pool the data across the six SNFs into the pre and post-PMC training periods to dilute the effect of facility variability. Given that the average length of stay in a SNF is 21 days, the pre/post PMC training design will consist of two independent samples of patients to include only those that were admitted and discharged within a given period. As we get interest from additional facilities, we may submit an addendum to include them. Additional sites would help inform sample size estimates for a potential future, cluster-randomization study design. During the 5-month pre-PMC training period, the rehabilitation therapists will treat patients per the current standard of care and a trained CNA (blinded) or PT/PTA (as necessary) will collect outcomes data at admission, weekly, and at discharge. Then, training on the PMC intervention will occur over a 2-month period. Any patients admitted or discharged in the SNF during the PMC training period will not be used. During the 5-month post-PMC training period, therapists will implement the PMC protocol and collect outcomes data as indicated previously (Figure 1).

The medical records will provide information on prior level of function, age, other medical conditions, **re-hospitalization** and **emergency room visits**, medications, sex, admitting diagnosis, **falls**, SNF length of stay, **discharge location**, evaluation and treatment documentation.

Five focus group discussions of 4-6 therapists each will follow an interview guide and last a duration of approximately 1 hour. Therapist participation is voluntary, and all participants will be asked for informed consent. Discussions will be recorded and transcribed for content analysis.

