## **IV. Research Methods**

### **A. Outcome Measure(s):**

During both the pre-PMC and post-PMC training periods, a trained Certified Nursing Assistant (CNA) (blinded) will assess gait speed, TUG, and SPPB within 24-48 hours of admission to SNF. If the CNA is unable to assess within 24-48 hours of admission, then the physical therapist performs the assessments. The occupational therapist will administer the Mini Mental Status Scale to assess baseline cognitive status within 24-48 hours of admission to SNF. A trained CNA (blinded) will continue to perform functional assessments (gait speed, TUG, SPPB) weekly and at discharge from SNF (Figure 2). Physical therapists (PTs) and physical therapist assistants (PTAs) will perform weekly and discharge assessments as necessary.

Interventions: During the 5-month pre-PMC training period (baseline), all current patients at the SNF will receive usual care treatment as facility therapists will practice per current standard of care. We will collect pre-PMC training data for 3 months or until collection of data on 602 patients (half the number of patients approved to be consented) (Figure 1). Therapists will then be trained on the PMC intervention for 2 months. After training, the facilities and individual therapists will decide how to implement such care at their discretion. Following the training period, we will collect post-PMC training data for 5 months or until collection of data on 602 patients (half the number of patients approved to be consented) (Figure 1). The data collected in all facilities during the pre-PMC training period will be pooled into one group to dilute the effect of facility variability. The data collected during post-PMC training period will be pooled in the same way.

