#### **B. Description of Population to be Enrolled:**

Patients will be enrolled from four SNFs in the Denver metro area: **Gardens on Quail, Brookdale Mountain View, Veterans Community Living Community at Fitzsimons, and Powerback Rehabilitation; and two in Minnesota: Good Sam-Ambassador and Villa St. Louis Park.** All patients temporarily residing in the designated SNFs will receive the current standard of care during the 5-month pre-PMC training period. Outcomes data will be collected for all patients who are admitted and discharged during the 5-month pre-PMC training period. Once SNF staff have been trained on the PMC protocol (2-month period), all patients will receive the PMC intervention (post-PMC training period) as the new standard of care per therapist discretion, unless contraindicated. Outcomes data will be collected for all patients who are admitted and discharged during the 5month post-PMC training period. All patients will receive the respective intervention (current standard of care or PMC) until discharge from the SNF. Outcomes data will only be collected on patients who fit the inclusion criteria: adults older than 18 years of age who are admitted to a skilled nursing facility and receive at least physical or occupational therapy. Exclusion criteria: Patients with neurological disorders, such as a stroke or traumatic brain injury, will be excluded as the best practice for managing these patients is based on motor-control theory versus the proposed progressive strengthening and aerobic approach. Patients on hospice care will be excluded as hospice care is focused on palliative needs and not rehabilitation. Other patients to be excluded will include those with conditions where strength training is contraindicated (as indicated by the American College of Sports Medicine Guidelines for Exercise Testing and Prescription): recent unstable fractures, advanced congestive heart failure (ejection fraction <30%), bone metastasis sites, tumors in strengthening target areas, acute illness, recent myocardial infarction (within 3-6 weeks), weight bearing restrictions on graft or fracture sites, exposed tendon or muscle, absence of pedal pulses, presence of a fistula, and platelet levels <50,000/ $\mu$ L.

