#### **F. Data Analysis Plan:**

##### Analysis

[figure not shown]
**Primary and Secondary Outcomes:** **The primary outcome (Aim 1) for this study is the change in gait speed between admission and discharge from a SNF. The change in gait speed will be pooled across the six facilities for the two respective time periods (pre and post PMC training).** The mean **change in gait speed** for the independent group of patients tested during the pre-PMC training period will be assessed and compared to the mean change in gait speed for the independent group of patients during the post-PMC training period.

Secondary outcomes include physical function measures (SPPB, TUG) and health care utilization outcomes (emergency room visits, falls, skilled nursing home length of stay, and re-hospitalizations), which will be recorded weekly and at discharge from SNF. Preliminary descriptive and graphical analyses (including boxplots, scatterplots, profile plots to examine change over time) will be used for data cleaning and visualization of primary and secondary outcomes.

**Primary Analysis:** The primary analysis will be an intent-to-treat comparison of change in gait speed from SNF admission to discharge between 2 independent groups of patients (pre and post-PMC training groups). Statistical inference regarding the difference between pre and post-PMC training groups will be based on independent sample t-tests. Comparisons will be made on changes in outcome measures (admission to discharge)

within pre/post PMC training groups. Groups of patients will be pooled from all facilities to form 2 independent samples for comparison of time periods (pre and post PMC training) (See Figure 3). The conclusion about the statistical significance of differences between pre/post groups will be determined by this single statistical test to protect against an elevated risk of false positive conclusions.

**Figure 3.** Data analysis plan

**Secondary Analyses (Aim 2):** We will estimate health care utilization outcomes rates (falls, emergency department visits, skilled nursing home length of stay or re-hospitalizations) for each pre/post PMC training period and compare rates between arms using a likelihood ratio test.

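### Using only stays completed inside a fixed window right-truncates length of stay: the mean is understated and a pre/post difference can be distorted, even with two equal 5-month windows

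*Combined protocol and SAP*

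**What the plan says.** - **Sample rule.** Section C, Study Design and Research Methods, builds the comparison on "two independent samples of patients to include only those that were admitted and discharged within a given period". It adds: "Any patients admitted or discharged in the SNF during the PMC training period will not be used". The reason given is that the "average length of stay in a SNF is 21 days".
- **Same rule in both periods.** Section B, Description of Population, states it for the pre period ("Outcomes data will be collected for all patients who are admitted and discharged during the 5-month pre-PMC training period") and for the post period ("Outcomes data will be collected for all patients who are admitted and discharged during the 5month post-PMC training period").
- **Outcomes analysed on that sample.** Section F, Data Analysis Plan, lists length of stay, falls, emergency visits and re-hospitalizations as secondary outcomes. For Aim 2 it says: "We will estimate health care utilization outcomes rates (falls, emergency department visits, skilled nursing home length of stay or re-hospitalizations", with a likelihood ratio test between periods. The denominator of the rates is not defined. No follow-up beyond the window, censoring or time-to-discharge method is given.
- **Expectation.** The opening summary says length of stay will be recorded but is not expected to change under PMC.
- **Window length.** Section A, Outcome Measure(s), calls the pre period 5 months but also says "We will collect pre-PMC training data for 3 months or until collection of data on 602 patients". For the post period it says "we will collect post-PMC training data for 5 months or until collection of data on 602 patients".

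**The concern.** A patient enters the data only if discharge comes before the window closes. Someone admitted three weeks before the close is kept if the stay is short and lost if it is long, so the longer the stay, the more likely it is to be dropped. Length of stay is then estimated from a sample selected on length of stay, and equal windows do not cure this.

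Three things are at stake. Reported mean stay will be too low. A real change in stay after PMC training may be misread. In-stay events will be counted with long-stay patients under-represented, and what that does depends on a denominator the plan leaves open. Section C also says that data from further sites would inform sample sizes for a possible cluster-randomized study, so biased stay figures could carry forward into that planning.

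**Working it through.** The plan gives no figure for length of stay under this rule, so there is nothing to reproduce. Its one power calculation concerns gait speed and does not bear on this point.

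**Inputs.** From the plan: mean stay 21 days and a 5-month window in each period. Assumed: 5 months = 152 days, 3 months = 91 days, even admissions, and a CV of 0.5 to 1.0, because the spread of length of stay is not in the documents. A gamma distribution with shape k has CV = 1/√k, so shapes 1, 2 and 3 have CV 1.0, 0.71 and 0.58.

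**1. Share of admissions kept.** With window W and mean μ, a stay of length L is kept with probability 1 - L/W. On average this is 1 - μ/W = 1 - 21/152 = 0.862, so about 14% are dropped.

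**2. Observed mean.** The density of kept stays is proportional to f(L)(W - L). If almost no stay exceeds W, the observed mean is μ - σ²/(W - μ):

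| CV | SD (days) | 21 - SD²/131 | Bias |
|---|---|---|---|
| 0.5 | 10.5 | 20.16 | -4% |
| 0.75 | 15.75 | 19.11 | -9% |
| 1.0 | 21 | 17.63 (17.65 by integration) | -16% |

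Lognormal stays give 20.16, 19.13 and 17.88. Simulated gamma stays (1,000,000 admissions each) agree: 20.16 at CV 0.5 and 17.66 at CV 1.0.

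**3. A true pre/post difference, equal windows.**
- *Same CV in both periods (SD rises with the mean).* A true fall from 21 to 19 days is read as 1.36, 1.67 and 1.78 days for gamma shapes 1, 2 and 3, that is 0.68, 0.84 and 0.89 of its size.
- *Pure 3-day shift, shape unchanged.* It is read as 2.96 days, almost no shrinkage.
- *Spread differs between periods (gamma):*

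| Pre mean/SD | Post mean/SD | True difference | Observed |
|---|---|---|---|
| 20/15 | 22/13 | +2.0 | 20.7 - 18.3 = +2.4 |
| 21/15.75 | 18/18 | -3.0 | 15.6 - 19.1 = -3.5 |
| 21/21 | 20/10.5 | -1.0 | 19.2 - 17.7 = +1.5 |

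- *Identical distributions.* Both means fall by the same amount, so no false difference arises.

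**4. Patient-days.** The share of patient-days belonging to dropped stays is about μ(1 + CV²)/W. At CV 1.0 this is 21 × 2/152 = 28%; at shape 3 it is 21 × 1.333/152 = 18%. Dropped stays average 28 days (shape 3) to 42 days (shape 1), against 21 overall. A dropped stay of length L contributes on average L²/(2W) days before the close, out of L²/W in total. So about half of these days, 9-14% of the total, lie inside the window and can be recovered by censoring.

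**5. In-stay events.** At a constant daily hazard, events per stay fall in proportion to mean stay, while events per patient-day are unbiased. The re-hospitalized share can move either way. Take a true 18% (the hospitalized share in the opening summary) and CV 0.75:
- Re-hospitalized stays averaging 10 days, others 23.4: kept with probability 0.934 and 0.846, so the observed share is 0.18 × 0.934/(0.18 × 0.934 + 0.82 × 0.846) = 19.5%.
- Re-hospitalized stays averaging 28 days, others 19.5: kept with probability 0.816 and 0.872, giving 17.0%.

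**6. Unequal windows.** With 91 days before and 152 days after and no true change, gamma means are read as 19.4 vs 20.2 (CV 0.5), 17.5 vs 19.1 (CV 0.75) and 15.2 vs 17.7 (CV 1.0), a spurious rise of 0.7 to 2.5 days.

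**The case against.** A reader might infer that truncation always shrinks a pre/post difference and so biases the trial toward finding no change in stay. The documents do not support that. They give no spread for length of stay in either period, and the direction depends on it: the last three rows tabulated above show enlargement and reversal. Hypothesis 2 itself gives a reason for the shape to change, since fewer early re-hospitalizations would remove some short stays. The planned test is also not an equivalence test. Truncation reduces the SD as well, so for 21 vs 19 days the standardized difference falls by only about 6-17% (shapes 3 to 1).

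A second tempting reading is that all in-stay event rates are biased. That is not shown. Loss of patient-days costs precision; bias depends on the denominator and on whether risk is constant over the stay.

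On materiality, length of stay appears in neither aim nor hypothesis, the plan does not expect it to change, the study is described as preliminary, and the conclusion on significance rests on the single gait-speed test. The sample rule also has a purpose: it keeps the two groups independent and keeps discharge tests taken during training out of the primary comparison. All of this stands. It limits the severity and the scope of any remedy, but does not remove the bias in mean stay.

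The magnitudes rest on even admissions, while the plan itself mentions variable monthly census, and the 602-patient limit could close a window early. Uneven admissions would change the figures; the dependence of inclusion on length of stay would remain.

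**Conclusion.** The concern holds in a limited form. Length of stay is right-truncated by the sample rule, nothing in the plan corrects this, and equal windows do not remove it. With a 21-day mean, a 152-day window, even admissions and CV 0.5 to 1.0, about 14% of admissions are lost and mean stay is understated by about 4-16%. A true difference is typically attenuated when SD rises with the mean, but its distortion has no fixed direction when spread changes. Events per stay and the re-hospitalized share can be distorted; events per patient-day are not, at constant hazard. No effect on the primary gait-speed analysis is claimed. Severity is low to moderate.

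**What to change.** 1. Leave the primary gait-speed analysis and its sample rule in section C unchanged. Relaxing that rule for the whole study would let discharge gait tests taken during training into the primary comparison.
2. For length of stay and in-stay events only, define each group by admission date inside the window. Censor stays still open at its end: the start of training for the pre group, the end of month 5 for the post group.
3. Analyse length of stay as time to discharge, with discharge to the community and transfer to hospital as competing exits, and report cumulative incidence. This also handles the Aim 2 community-discharge outcome, for which censored stays have no destination. A single time-to-discharge curve would merge going home with going back to hospital.
4. State that falls, emergency visits and re-hospitalizations are reported per patient-day up to the censoring date.
5. Optionally, keep these patients' weekly gait speeds up to that date in the repeated-measures trajectory model of section F.
6. Use the same window length in both periods, reconcile the 3-month and 5-month text in section A, and state how the 602-patient limit closes a window.

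The cost is plan wording and some extra analysis. No new tests are needed: function is assessed weekly, events come from medical records, and a patient's discharge date is unknown while these data accrue. The small downside is that length of stay is reported as a survival or cumulative-incidence summary instead of a simple mean.

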# **Shifting Rehabilitation Paradigms in Skilled Nursing Facilities**

**NCT: 02927171**

**Version Date: 12.06.2018**

Each year Medicare spends approximately \$31.3 billion on 2.4 million skilled nursing facility (SNF) episodes of care. SNFs rely on interdisciplinary approaches to patient care to maximize rehabilitation potential for return to prior level of function and reduce the risk of adverse events in older adults. However despite a substantial increase in spending on SNF services and minimal change in complexity of the caseload, 68% of patients are below their pre-hospitalization level of function at discharge, 25% return to the community, and 18% are hospitalized. This may be partially explained by current SNF approaches to patient care which foster inactivity and participation in low intensity rehabilitation interventions (preliminary data). Both inactivity and low-intensity interventions may perpetuate further functional decline or impede maximal recovery. The serious implication of risk with functional decline is exemplified by studies which have shown declines in physical function can increase the risk of being re-hospitalized six-fold and may infer other long term effects such as increased risk for mortality, morbidity, and institutionalization. Muscle weakness, reduced cardiorespiratory reserve, and neuromuscular deficits have been attributed to this acute decline in function. However current rehabilitation strategies in SNFs do not promote adequate dose and mode of interventions to induce beneficial systemic adaptations, perhaps due to the lack of evidence on effective rehabilitation protocols for this medically-complex population. In addition, the lack of standardization across rehabilitation practices makes it difficult to discern which treatment approaches are the most effective. We propose to implement a standardized, progressive, multi-component program (PMC) to address this gap in research and clinical practice. The study will be completed concurrently in two SNFs and consist of three periods: 5 month pre-PMC training period, 2 month PMC training period, and 5 month post-PMC training period (Figure 1). We increased the data collection period from 3 to 5 months due to the variability in month to month census at the SNFs. The data from each facility will be pooled into the respective time period to dilute the effects of facility variability. Given the high turnover of patients in SNFs (average length of stay ~21 days), the analysis will consist of independent 2-sample t-tests. During pre and post PMC training periods, measures of physical function will be assessed on all patients weekly and at discharge from SNF. Any hospitalizations or emergency room visits and falls will be obtained from the medical record and documented. The discharge location of all patients will be documented. The length of stay will be recorded, but given the current reimbursement model, the average length of stay is not expected to change with implementation of PMC.

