
## I. Hypotheses and Specific Aims:

**Specific Aim 1:** To determine if the group in the post-PMC training period demonstrates better physical function, as measured by *gait speed* (primary outcome), timed-up-and go test (TUG), and the Short Physical Performance Battery (SPPB) compared to pre-PMC training period.

Hypothesis 1: Patients in the post-PMC training period will demonstrate greater improvements in gait speed, TUG, and SPPB at time of discharge from SNF (primary endpoint) compared to the group in the pre-PMC training period.

**Specific Aim 2:** To determine if the group in the post-PMC training period demonstrates improved rates of discharge to the community from SNF facilities and lower hospital re-admission rates compared to pre-PMC training period.

Hypothesis 2: Following the post-training PMC period, patients will demonstrate higher rates of discharge to the community and have a lower frequency of hospital re-admissions during SNF stay compared to the pre-PMC training period.

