treating therapists or nursing staff. Falls will be defined as an unintentional change in position resulting in coming to rest on the ground or other lower level.

Covariates, clinical and background characteristics. Information on other patient characteristics to describe the patient population and interpret results will be obtained from facility medical records; all data will be de-identified. These characteristics include age; gender; race; history of comorbidities, medications, primary diagnosis for hospital admission; length of skilled nursing facility stay; complications in hospital and length of stay.

Qualitative data will be collected through voluntary focus group discussions consisting of therapists in the SNFs with current IRB approval (Brookdale Mountain View, Veterans Community Living Center at Fitzsimons, PowerBack Rehabilitation, Gardens on Quail, Good Sam-Ambassador, Villa St. Louis Park). The data collected will inform future refinement of the PMC program for large-scale dissemination.

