### G. Summarize Knowledge to be Gained:

Rehabilitation therapy is known to help improve function in older adults after an acute functional decline. However, we do not know if there is an additional benefit to implementing a progressive program with an emphasis on activity throughout the day in the SNF setting. Effective rehabilitation interventions in SNFs can improve function in adults, which allows patients to return to prior level of care and location. This study has the potential to not only improve individual functional outcomes but also increase community discharge rates and reduce hospital readmissions. The alternative treatment is to choose a different skilled nursing facility (non-research site) which employs a different standard of care.

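### Aim 2 compares community discharge between two unrandomised periods, but where patients lived before hospital is neither a named data item nor part of any planned adjustment

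*Combined protocol and SAP*

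**What the plan says.** Section I, Hypothesis 2, predicts that after training "patients will demonstrate higher rates of discharge to the community". The opening summary adds that "The discharge location of all patients will be documented".

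Section IV.B admits "adults older than 18 years of age who are admitted to a skilled nursing facility and receive at least physical or occupational therapy". The exclusions that follow are clinical, and none concerns where the patient lived before the hospital stay. The nearest wording on residence is descriptive: "All patients temporarily residing in the designated SNFs will receive the current standard of care".

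Two places list the patient data to be collected:

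- Section IV.A, covariates paragraph: "These characteristics include age; gender; race; history of comorbidities, medications, primary diagnosis for hospital admission; length of skilled nursing facility stay", followed by hospital complications and length of stay.
- Section IV.C: "The medical records will provide information on prior level of function, age, other medical conditions", followed by items that include discharge location and, as an open-ended source, "evaluation and treatment documentation".

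Neither names pre-hospital residence.

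Section IV.C describes two independent patient samples, one per period, pooled over six facilities. Section IV.F compares Aim 2 rates between periods with a likelihood ratio test. It states no adjustment, and its list of outcomes (falls, emergency visits, length of stay, re-hospitalizations) omits community discharge. Section IV.G describes the benefit of effective rehabilitation as something "which allows patients to return to prior level of care and location".

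**The concern.** Whether a patient can be discharged to the community depends heavily on whether the patient came from there. Someone admitted from long-term care who goes back to it has regained the prior location, which is the benefit Section IV.G describes, yet would count against Hypothesis 2. The items the plan names cannot separate that patient from a community-dweller who was newly institutionalised.

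There are two consequences. If the share of institution-origin patients is the same in both periods, the contrast is diluted by people in whom the event is unlikely whatever the therapy. If the share differs, the crude rates differ even when PMC does nothing. Randomisation does not protect against this here, and the plan gives reasons why case mix might move. The opening summary cites month-to-month variation in census. Section IV.F (sample size) reports more variability between facilities than expected, with patient population as an example, and the same section and Section IV.C allow for added facilities.

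**Working it through.** **Plan's own figure.** There is none to reproduce. The only power calculation is for gait speed, and no expected rate, difference or sample size is given for community discharge.

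**Inputs from the documents.**
- Community-return rate 25% (opening summary), used as the pre-period rate.
- 602 patients per period (Section IV.A). This is an upper limit on data collection, not an analysis size for this outcome.

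**Assumptions.**
- q, the share admitted from an institution, in each period. The documents give no value, so a range is shown.
- r_i, the community-discharge rate among institution-origin patients: 0%, with 5% as a sensitivity value.
- No PMC effect: origin-specific rates are the same in both periods.
- A two-sided 5% unadjusted test of two proportions, the large-sample equivalent of the likelihood ratio test.

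**Formulas.** Overall rate p = (1 − q) × r_c + q × r_i, where r_c is the rate among community-origin patients. Fixing p_pre = 0.25 gives r_c = (0.25 − q_pre × r_i) / (1 − q_pre). Then p_post = (1 − q_post) × r_c + q_post × r_i, SE = sqrt[(p_pre(1 − p_pre) + p_post(1 − p_post)) / 602] and z = (p_post − p_pre) / SE. The chance of rejection is approximately 1 − Φ(1.96 − |z|), plus a small opposite tail.

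**One case in full (15% to 5%, r_i = 0).** r_c = 0.25 / 0.85 = 0.294. p_post = 0.95 × 0.294 = 0.279. Difference = 0.029. SE = sqrt[(0.1875 + 0.2013) / 602] = 0.0254. z = 1.16. Rejection about 21%.

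**Range, falling institutional share.**

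| q pre → post | Spurious difference, r_i = 0 | Rejection | Spurious difference, r_i = 5% | Rejection |
|---|---|---|---|---|
| 10% → 5% | +1.4 points | 9% | +1.1 points | 7% |
| 15% → 5% | +2.9 points | 21% | +2.4 points | 15% |
| 20% → 10% | +3.1 points | 23% | +2.5 points | 17% |
| 30% → 15% | +5.4 points | 55% | +4.3 points | 39% |
| no change | 0 | 5% | 0 | 5% |

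**Opposite direction.** If the share rises from 5% to 15% with r_i = 0, then r_c = 0.25 / 0.95 = 0.263 and p_post = 0.85 × 0.263 = 0.224. That is a spurious fall of 2.6 points, rejected about 19% of the time.

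**Dilution with a stable mix.** If PMC adds D points among community-origin patients and nothing among the rest, the all-patient difference is D × (1 − q). For example, D = 5 and q = 15% gives 4.25 points.

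**Scale.** With 602 per period, 80% power from a 25% baseline needs a rise of about 7.3 points: SE = sqrt[(0.1875 + 0.2187) / 602] = 0.0260, and 0.073 / 0.0260 = 2.8. The spurious differences above are smaller than that, but not negligible beside it.

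**With the fix.** Comparing community-origin patients only sets r_c against r_c, so in every row the difference is 0 and the error rate is the nominal 5%.

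**The case against.** Several stronger readings are tempting, and the documents do not support them.

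- *Prior residence will not be captured.* The plan does not say that. The covariate list is introduced as inclusive, the records used include "evaluation and treatment documentation", and Section IV.D leaves field-level detail to a data dictionary that is not reproduced. What can be said is that the item is not named. Nor is it beyond recovery, since the proposed back-fill relies on those same records.
- *The plan fixes the denominator as all patients.* It says discharge location is documented for all patients. It writes down no denominator and specifies no analysis of community discharge. All patients is the natural reading, not a stated rule.
- *A higher post-period rate would be an artefact.* Bias needs a shift in mix. Nothing in the documents shows that one occurred or gives its size, and a shift could equally hide a benefit.
- *The false-positive rate is above 50% for a moderate shift.* With an assumed 60% return rate among community-origin patients, institutional shares of 15% and 5% give 51% and 57%, z = 2.09 and about 55% rejection. The documents' own 25% gives about 21% for the same shift. Reaching 55% from that base takes a fall from 30% to 15%, which is large for the same pooled facilities two months apart.

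Three further points have force. Neither community nor institution is defined; if assisted living counts as community, the 0% assumption fails for those patients. The description of patients as temporary residents, and the requirement to be admitted and discharged within a period, may keep out some long-stay residents, though neither is a residence criterion or covers people who came from another institution. And the all-patient rate is a legitimate quantity, of the kind the opening summary itself quotes. Replacing it would be a choice of estimand rather than a correction, so it should stay.

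**Conclusion.** The concern holds in a limited form. As written, the plan would give a community-discharge comparison that is diluted by institution-origin patients and open to confounding by their share, with no named item or planned adjustment to deal with either. The likely size cannot be derived from the documents. Under the stated assumptions, falls in institutional share of 5 to 15 points produce spurious gains of about 1 to 5 points and rejection rates of about 7% to 55% against a nominal 5%. The top of that range needs the most extreme shift shown, and an unchanged mix gives no bias.

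A reader might infer that the trial's main conclusion is at risk. It is not: Section IV.F rests significance on the single gait-speed test, community discharge is secondary, and Section IV.C calls the study preliminary. This is a worthwhile improvement to Aim 2, not a threat to Aim 1.

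**What to change.** 1. Name pre-hospital residence (community or institution) as a medical-record item in Sections IV.A and IV.C, with back-fill for patients already abstracted where the records allow.
2. Define community, stating how intermediate settings such as assisted living are classed.
3. Add community discharge to the Aim 2 outcomes in Section IV.F and state its denominator.
4. Keep the all-patient rate, and beside it compare the periods among community-origin patients, or stratified by or adjusted for origin.
5. Report the institutional share in each period and, for institution-origin patients, the proportion who returned to their prior residence.

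The cost is one more field from a record already being abstracted, the back-fill effort, and a few sentences in the analysis plan. The restricted comparison has a somewhat smaller denominator, and residence may be missing for some patients already discharged, which should be reported.
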